7.3 Source documents

Source documentation will be maintained at the site. Source documents, which may include worksheets, patient medical records, QoL questionnaires must be created and maintained by the investigational site team. The investigator will clearly mark clinical record to indicate that the subject is enrolled in this study. The data reported on the CRFs shall be derived from source documents and be consistent with these source documents, and any discrepancies shall be explained in writing.

Where copies of the original source document as well as printouts of original electronic source documents are retained, these shall be signed and dated by a member of the investigation site team with a statement, that it is a true reproduction of the original source document.

The PI and/or institution shall permit Medtronic, the CRO and regulatory bodies direct access to source data and documents, taking into account any restrictions due to local law, to perform study-related monitoring, audits, EC/IRB review and regulatory inspections.

7.4 Study Deviations

A study deviation is defined as any incompliance to the Clinical Investigation Plan or the Clinical Trial Agreement.

All study deviations must be reported on the Case Report Form regardless of whether medically justifiable, pre-approved by Medtronic, an inadvertent occurrence, or taken to protect the patient in an emergency. Examples of study deviations are:

- Missing/incorrect data
- Missed PIC/PDRF sign off, incorrect PIC/PDRF version signed
- Incorrect version of the consent form provided to the patient
- CIP required training deviations
- CTA violations (e.g. enrollment started before CTA)
- EC approval not obtained before starting the study
- Patient enrolled during lapse of EC approval
- Informed consent not obtained prior to participation in the study
- Incorrect version of the consent form provided to the subject
- Enrolled subject did not meet inclusion/exclusion criteria
- Unauthorized physician or study personnel performing study procedures

Deviations from the CIP, which are outside the EBogen system, can be controlled by monitoring visits. Queries and discrepancies found at a monitoring visit will be handled according to the Monitoring Plan.

Deviations in the EBogen system are handled through emails sent to the site and might be explained within remote monitoring calls to the sites (see chapter 7.5).

Study deviations need to be documented in eCRF "Deviation Form" which contains following data:

- Administrative information (e.g. CaseNo for patient identification, site ID; date of Deviation)
- Deviation description
- Reason for Deviation
- Action taken

The eCRF "Deviation Form" can be completed by the site personnel or by the sponsor of designee in cooperation with the site personal and has to be signed by authorized site person.

Data entered in the EBogen system is checked for completeness and accuracy of data entry, directly. By default, all fields are marked as required. However, with the exception of the first page containing the stratification and eligibility questions, the navigation in the CRF is not restricted, even if fields are missing or contain invalid data. All fields that are optional have been assigned an "NA" checkbox or a similar option to specify that this field is not available. Checking this "NA" option will disable the original data entry field to signal that the value is not available. Fields that are foreseen for specific investigations (non-mandatory investigations) are only available when the leading question has been marked "yes", or the obvious corresponding choice was made. Depending on the layout and size of the fields these conditional fields will be either disabled or made invisible until the appropriate prerequisite is fulfilled.

7.5 Monitoring

It is the responsibility of the Sponsor to ensure proper monitoring of this clinical investigation per regulations. Trained Medtronic personnel or delegates appointed by Medtronic may perform study monitoring at the study center in order to ensure that the study is conducted in accordance with the CIP, the Clinical Trial Agreement, and applicable regulatory and local requirements.

Medtronic, or delegates, must therefore be allowed access to the patients' case histories (clinic and hospital records, and other source data/documentation) upon request as per the Subject Informed Consent, Research Authorization (where applicable) and Clinical Trial Agreement. The Monitoring Plan will be maintained separate from the Clinical Investigation Plan.

Frequency of monitoring visits will be based upon patient enrollment, duration of the study, study compliance, number of adverse events, findings from previous monitoring visits and any suspected inconsistency in data that requires investigation. The principal investigator shall be accessible during monitoring visits. Monitoring for the study will be done in accordance to the study Monitoring Plan. Site initiation and closure visits will be performed by Medtronic or designee. Monitoring visits may be conducted to assess site study progress, the PI's adherence to the CIP, regulatory compliance including but not limited to EC/IRB review and approval of the study, maintenance of records and reports, and review of source documents against subject CRFs. Monitors may work with study personnel and the site's PI to determine appropriate corrective action recommendations and to identify trends within the study or at a particular site.

7.5.1 . Access to study site and study materials

The PIs, his/her delegate(s) and the study coordinator(s) shall be accessible to Medtronic clinical personnel and or CRO delegate. This accessibility is of particular importance for reviewing data in the CRF. Direct access to patient records for source data verification will be granted and prepared prior to any monitoring visits.

7.5.2 Audits and study site inspections

Medtronic may choose to perform random audits throughout the study as part of quality assurance. The purpose of an audit is to verify the adequate performance of the study related activities, independently of the employees involved in the study. Regulatory bodies may also perform inspections at participating study sites.

The PI and/or institution shall permit Medtronic and regulatory bodies direct access to source data and documents, taking into account any restrictions due to local law, to perform study-related monitoring, audits, EC/IRB review and regulatory inspections.

In addition, when applicable, the study sites may be inspected by the competent authority. Any competent authority announcements shall be forwarded to Medtronic study management immediately. Study sites will be required to provide access to source documents and data to the regulatory bodies and competent authority.

Monitoring visits will be conducted in accordance to the Monitoring Plan.

8 Reimbursement

Compensation according to local regulations and to the time spent to inform patients and to document patient data will be paid. Reimbursement conditions will be documented in the Clinical Trial Agreement.

9 Registration

This study will be publicly registered prior to first enrollment in accordance with the 2007 Food and Drug Administration Amendments Act (FDAAA) and Declaration of Helsinki 2013 (30) on <http://clinicaltrials.gov>.

10 Good Clinical Practice

This registry will be conducted according to the rules of Good Clinical Practice (GCP) (31). These include the protection of the rights, safety and well-being of human subjects, controls to ensure the scientific conduct, credibility and data integrity of the clinical investigation, and the definition of responsibilities of the sponsor and investigators.

11 Adverse Events

The products used in the study are market released in all geographies and used within the current indications for use as indicated in the product labeling. Foreseeable adverse event information is provided in the product labeling documentation. The collection of adverse event (AE) for reporting will be performed according to local requirements for observational studies. To achieve the study objectives, AE data relevant to the study objectives need to be collected.

All procedure-related and system-related AEs will be collected throughout the study duration, starting at the index procedure.

AE information will be reported to Medtronic upon site awareness on an Adverse Event Form, including a description of the AE, date of AE onset and PI awareness, diagnostics, symptom's description, treatment, resolution, and assessment of both the seriousness and the relatedness to the device. For Serious Adverse Events that require immediate reporting, initial reporting may be done by phone, fax, email (see section "Directory" for Medtronic contact details), or on the CRF completing as much information as available. The original completed AE CRF must be reported to Medtronic as soon as possible. If AE is not resolved at the moment of completeness, AE update needs to be completed upon AE resolution. All efforts should be applied to follow unresolved adverse events until they has been resolved, is unresolved with no further actions planned, the patient exits the study or until study closure, whichever occurs first.

An Adverse Event inherent to a surgical procedure that is expected to occur in all subjects for a projected duration according to the investigator's opinion, including, but not limited to the list of unavoidable AEs provided in Table 11-1.

Unavoidable AEs are not reportable AEs. Onset of any of these events occurring after the specified timeframes and/or events lasting longer than the specified timeframe if onset is at the time of the surgery need to be reported (if it is procedure or devise related AE).

Table 11-1: Unavoidable Adverse Events Related to Ablation Procedure

| Name | Event Description Time Frame (Hours) from the Surgical Procedure |
|-----------------------------------------------------|------------------------------------------------------------------|
| Anesthesia related nausea/vomiting | 24 |
| Low-grade fever (<100 F or < 37.8 C) | 48 |
| Groin insertion/site pain | 72 |
| Mild to moderate bruising / ecchymosis | 168 |
| Sleep problems (insomnia) | 72 |
| Back pain related to lying on the table | 72 |
| Chest pain secondary to ablation (during procedure) | 4 |

11.1 Protocol defined Adverse Events

- Documented pre-existing conditions are not considered AEs unless the nature or severity of the condition has worsened.
- Unavoidable Adverse Events, listed in Table 11-1 need not be reported unless the adverse event worsens or is present outside the stated timeframe post-procedure.

Adverse events relevant to the clinical objectives are defined in Table 11-2.

Table 11-2: Adverse Event Definition

| General (including ISO 14155:2011 definitions) | |
|-------------------------------------------------------|--------------------------------------------------------------------------------------------------------------------------------------------------------------------------------------------------------------------------------------------------------------------------------------------------------------------------------------------------------------------------------------------------------------------------------------------------------------------------------------------------------------------------------------------------------------------------------------------------------------------------------------------------------------------------------------------------------------------------------------------------------------------------------------------------------------------------------------|
| Definition | Description |
| Adverse Event (AE) | 
Any untoward medical occurrence, unintended disease or injury, or untoward clinical signs (including abnormal laboratory findings) in patient, users or other persons, whether or not related to the investigational medical device
 
NOTE 1: This definition includes events related to the investigational medical device
 
NOTE 2: This definition includes events related to the procedures involved.
 
NOTE 3: For users or other persons, this definition is restricted to events related to investigational medical devices.
 
(ISO 14155:2011, 3.2)
 |
| Serious Adverse Event (SAE) | 
An adverse event that
 
a) led to a death,
 
b) led to a serious deterioration in the health of the patient that either resulted in
 
 • a life-threatening illness or injury, or • a permanent impairment of a body structure or a body function, or • in-patient or prolonged hospitalization, or • resulted in medical or surgical intervention to prevent permanent impairment to body structure or a body function 
c) led to fetal distress, fetal death or a congenital abnormality or birth defect.
 
NOTE: Planned hospitalization for a preexisting condition, or a procedure required by the CIP, without serious deterioration in health, is not considered a serious adverse event.
 
(ISO 14155:2011, 3.37)
 |
| Device deficiency | 
Inadequacy of a medical device with respect to its identity, quality, durability, reliability, safety or performance (ISO 14155:2011 3.15)
 
NOTE: Device deficiencies include malfunctions, use errors, technical observations and inadequate labeling.
 |
| Adverse Device Effect (ADE) | 
Adverse Device Effect (ADE): adverse event related to the use of an investigational medical device.
 
Note 1: This definition includes any adverse event resulting from insufficient or inadequate instructions for use or the deployment, implantation, installation, or operation, or any malfunction of the medical device.
 
Note 2: This definition includes any event resulting from user error or from intentional misuse of the medical device
 
(ISO 14155:2011, 3.1)
 |
| Serious Adverse Device Effect (SADE) | 
Adverse device effect that has resulted in any of the consequences characteristic of a serious adverse event.
 
(ISO 14155:2011, 3.36)
 |
| Unanticipated Serious Adverse Device Effect (USADE) | 
Serious adverse device effect which by its nature, incidence, severity or outcome has not been identified in the current version of the risk analysis report.
 
(ISO 14155:2011, 3.42)
 |

| Study required (reportable) AEs | |
|----------------------------------------|-----------------------------------------------------------------------------------------------------------------------------------------------------------------------------------------------------------------------------------------------------------------------------------------------------------------------------------------------------------------------------------------------------------------------------------------------------------------------------------------------------------------------------------------------|
| System Related AE | 
An adverse event that results from the presence or performance (Intended or otherwise) of the Phased RFA system component.
 
 • Catheter Related: An adverse event that results from the presence or performance (intended or otherwise) of the Phased RF catheters • Generator Related: An adverse event that results from the presence or performance (intended or otherwise) of the Phased RF generator 
Note: ISO defined ADE is part of Serious System related AEs.
 |
| Procedure Related AE | 
An adverse event that occurs due to index or Phased RFA re-ablation procedure.
 
 • Phased RFA Procedure Related: Event that occurs due to any procedure related to the Phased RFA procedure. • Procedure Related: Event that occurs due to any other procedure during the Phased RFA in the study (e.g. EP study, ICM implant). |
| Serious system or procedure related AE | 
An AE which full fill the definition of the procedure or system related AE combined with definition of seriousness (see above SAE).
 
Note: ISO defined SADE and USADE are part of Serious system related AEs.
 |

Reporting of ALL Serious Adverse Events is not part of the GOLD AF registry. Nevertheless, all geography specific AE reporting requirements (EC or regulatory reporting) should be followed. It is the responsibility of the PI to comply with any AE reporting requirements stipulated by EC/IRB with the applicable support provided by the sponsor.

AEs will be reviewed by Medtronic. This review will include the determination whether the AE meets country regulatory requirements. The sponsor will ensure timely AE reporting to meet global regulatory requirements.

11.1.1 Patient Death

Death classification:

1. Phased RFA system related
2. Phased RFA procedure related
3. Not study related

As soon as possible after the investigator first learns of the death, the CRF "Exit form" needs to be completed and the classification provided as per above.

In case the death is related to the Phased RFA system or Phased RFA procedure, a CRF "Adverse event" needs to be completed as a serious AE.

Regulatory reporting of the patient's death will be completed according to local regulatory requirements.

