procedure, sites will be asked to keep patients enrolled for 30 days to ensure potential procedure / device related AEs are assessed and collected. If there are no related.

All subject deaths must be reported by the investigator to Medtronic on an Exit Form as soon as possible after the investigator first learns of the death.

In the event of a patient's death, the investigator is responsible to assess at their own discretion whether or not the death is related to the procedure and/or the system.

If any relatedness is assessed, it is required also the completion and reporting of a Serious Adverse Event (SAE) form (see paragraph 11.1.1). Data collection requirements are summarized in Table 7-1 below.

Table 7-1: Data collection requirements at subject visits

| Data Collection* | Baseline | Procedure | General FU | 12 Months FU | 12 Months FU by phone |
|--------------------------------------|--------------------|------------------|-------------------|---------------------|------------------------------|
| Enrollment (PIC/PDRF) | X | | | | |
| Demographics | X | | | | |
| Medical History [#] | X | | | | |
| Concomitant disease | X | | | | |
| Diagnostics | X | | X | X | X |
| Symptoms | | | X | X | X |
| Medication list | X | | X | X | X |
| Administrative information | | X | X | X | X |
| Anticoagulation pre-intra-procedural | | X | | | |
| General procedure summary | | X | | | |
| Consumables | | X | | | |
| PVI confirmation | | X | | | |
| Hospital discharge | | X | | | |
| Quality of Life (AFEQT) | X | | | X | X |
| History of AF since last visit | | | X | X | X |
| Hospitalization | | | X | X | X |
| Reportable Adverse events** (AEs) | - Whenever occur - | | | | |
| Study Exit | - Whenever occur - | | | | |
| Study Deviation form *** | - Whenever occur - | | | | |

* prior to first patient enrollment every site needs to fill in a site questionnaire once #= Medical history includes questions about prior CVD, history of AF, main underlying disease, concomitant disease and history of AF.

** Data collecting requirement for Adverse Event eCRF described in chapter 11 "Adverse Event"

*** Data collecting requirement for Deviation eCRF described in chapter 7.4 "Study Deviations"

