11.2 Vigilance Reporting

All devices used in this study are market-released. Therefore, Post Market Surveillance and product complaint reporting is applicable to all market-released devices used in the study. The reporting of product complaints abuse, and misuse of these CE-labeled devices is not part of the study and should be done in addition to the AE reporting according to regional requirements.

11.3 Adverse Events Advisory Committee (AEAC):

At regular intervals, an independent Adverse Events Advisory Committee will conduct a medical review of the AEs for adjudication. The Committee will consist of a minimum of three non-Medtronic employed physicians that are not participating investigators for the study, including the AEAC chairperson.

The AEAC is responsible for reviewing the investigator's assessment and classification of AE. The AEAC will review AEs and provide a final adjudication of relatedness and seriousness and can advise on the provided diagnosis.

For seriousness only study reportable AEs will be adjudicated. Relatedness of the AEs can be adjudicated as not related to the procedure/system or classified according to the Table 11-2.

Study lead may facilitate and participate in AEAC meetings, but will be non-voting members. The safety Medtronic personnel or study manger will provide the AEAC with the PI's description and classification AEs under review.

If the AEAC disagrees with the investigator's classification of the event, the rationale will be provided to the investigator. If the investigator agrees with the AEAC, this will be documented accordingly. If the investigator does not agree with the AEAC classification, both determinations will be documented within the study report. However, the AEAC determination will be used for analysis purposes.

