## 8.2 Statistical analyses for additional objective

### 8.2.1 Estimate Phased RFA procedure safety

Major procedure related complications include vascular complications secondary to venous access, cardiac tamponade, embolic stroke, esophageal injury, phrenic nerve injury, PV stenosis, reentrant tachycardia arrhythmias arising from ablations, mainly left Afl.

Adverse events (AE) including their relatedness to the respective procedure, are documented starting from the first documented procedure until the 12 month FU. For this analysis only adjudicated AE data (SUO form) and coded AE data (from free text fields) will be used. In addition, TIA/Stroke events will be taken from general FU forms to calculate procedure safety. Analysis will be performed at 30 days and at 12 months after procedure.

If no adverse event was documented within the 12 month FU period, the patient or the procedure is considered to be "free of AE". AEs are documented in the AE form, whereby distinctions in relatedness to which procedure (index phased RFA, repeated phased RFA or phased RFA re-ablation) will be made. Phased RFA procedure relatedness will also be taken from the AE form (Relatedness to Phased RFA procedure = related). The documented date of the AE will be used to set the point in time. For analysis purposes, phased RFA procedure safety will be calculated for first documented procedures (on procedure and patient level), separated for additional procedures (on procedure level) and for patients with additional procedures (on patient level).

Procedure safety will be calculated for procedures that have been carried out (number of RF applications per patient > 0) and disregarding procedure successfulness. This study objective will be calculated for the BAS and the FAS (Appendix B) for patients with signed eCRF.

Further analysis might be performed, e.g. procedure safety for using PVAC GOLD solely or not PVAC GOLD solely (using other catheter or using adjunctive devices).

**Table 7:** Procedure safety variables at AE form

AE due to definition	eCRF field: AE description	Related FID's annotated eCRF (V1.3, V1.4)
Vascular access complication	Vascular access complication 
 
• Hematoma or
 
• Arterio-venous fistula or
 
• Femoral artery pseudoaneurysm
 
	F31000010_6

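### A death the investigator classes as not study related has no specified route to independent relatedness review, and death is not a listed safety outcome

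*Protocol*

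**What the plan says.** **Collection.** Protocol section 11 limits the events collected: "All procedure-related and system-related AEs will be collected throughout the study duration, starting at the index procedure". Section 11.1 adds: "Reporting of ALL Serious Adverse Events is not part of the GOLD AF registry".

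**Deaths.** Section 7.2 (Study Exit) says that after a death "the investigator is responsible to assess at their own discretion whether or not the death is related to the procedure and/or the system". It continues: "If any relatedness is assessed, it is required also the completion and reporting of a Serious Adverse Event (SAE) form". Section 11.1.1 gives three classes (system related, procedure related, not study related) and says of the Exit form that it "needs to be completed and the classification provided as per above". It then sets the condition for the adverse event form: "In case the death is related to the Phased RFA system or Phased RFA procedure, a CRF" for an adverse event is to be completed as serious.

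**Adjudication.** Section 11.3 has the AEAC review adverse events and the investigator's classification of them. On relatedness it says: "Relatedness of the AEs can be adjudicated as not related to the procedure/system or classified according to the Table 11-2". Where the investigator and the AEAC disagree, the AEAC determination is the one analysed.

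**Analysis.** SAP 7.2.4 restricts adverse event analysis to adjudicated events. SAP 8.2.1 says: "For this analysis only adjudicated AE data (SUO form) and coded AE data (from free text fields) will be used". It adds TIA/stroke from general follow-up forms, and treats a patient with no documented adverse event during the 12-month follow-up as free of adverse events.

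**The concern.** The AEAC exists so that the investigator's view of relatedness is not final. For deaths, however, that same view decides whether an adverse event form is required, and so whether the committee is sure to see the case. An error of over-attribution can be corrected on review. An error of under-attribution has no planned correction, because nothing in the plan brings the case forward.

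Death is the most serious safety outcome, and related deaths are likely to be so few that one case decides whether the report says none or some. Safety is a stated objective, so a reader of the final report would reasonably assume that related mortality had been independently reviewed in both directions. Under the current text that cannot be assumed.

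**Working it through.** The plan gives no figure for this point, so there is none to reproduce. The check is to follow a death through the forms.

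**Path A: the investigator sees some relatedness.**
1. The Exit form is completed and the death is classed as system or procedure related.
2. An adverse event form is required (protocol 7.2 and 11.1.1).
3. The AEAC reviews it and may confirm it, reclassify it within Table 11-2, or find it unrelated (protocol 11.3).
4. The adjudicated result is analysed (SAP 7.2.4, 8.2.1).

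**Path B: the investigator sees none.**
1. The Exit form is completed and the death is classed as not study related.
2. No adverse event form is required.
3. Nothing in protocol 11.3 sends Exit forms, or deaths as such, to the AEAC.
4. The case has no adjudicated record, so SAP 7.2.4 does not select it. The coded free text in SAP 8.2.1 gives no way round this, because SAP Table 7 takes it from the adverse event form.
5. With no adverse event documented, SAP 8.2.1 read literally counts the patient as free of adverse events for the 12-month period, although the patient died during it.

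**Where death appears in the SAP.** It is not listed in Table 7 or Table 8. It can appear through the Study Exit tables (Appendix B), the vital status item on the 12-month form (4.3) and the discharge categories (Appendix D). None of these is a procedure-safety rate.

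**The exception.** SAP 8.2.1 and Table 8 take TIA/stroke from follow-up forms and state no relatedness condition. Protocol 7.2 asks for a General FU form as well as the Exit form after a death. A fatal stroke called unrelated therefore has a route into the safety analysis. A fatal event of another kind does not, and neither does a non-fatal, non-stroke event called unrelated.

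**The analysis set.** SAP 8.2.1 runs safety in the Baseline Analysis Set (BAS) and the Full Analysis Set (FAS), but the planned Kaplan-Meier safety graph (SAP Table 13) uses the FAS only. The FAS needs a valid signed 12-month form (SAP 4.3). A patient who dies before the 12-month window may have none, and would then be missing from that graph even if the death was related.

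**Scale, as illustration only.** The inputs are the planned size (about 1000 enrolled, 800 used for the precision statement) and the 3.9% overall complication rate cited in protocol 4.4.2.
- One missed patient: 1/1000 = 0.10 percentage points; 1/800 = 0.125 points.
- Expected patients with complications at 3.9% of 1000: 39. Assuming 1 to 3 missed patients, 1/39 = 2.6% to 3/39 = 7.7% in relative terms.
- Sampling error for comparison: 1.96 × √(0.039 × 0.961 / 1000) = 1.2 points.

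The number missed is an assumption. The illustration also assumes that the missed patient has no other adverse event form. If, say, an esophageal injury had already been filed, the patient-level rate would not change.

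**The case against.** The best defence is that collecting only related events is an openly stated scope choice for an observational post-market registry, and that the safety objective in protocol 4.4.2 concerns procedure- and device-related events. Deaths are not hidden: each is classified on the Exit form and Study Exit is tabulated in every analysis set. The threshold in protocol 7.2 is any relatedness, which is low. Monitors may compare source documents with the forms, and the case report forms and Monitoring Plan are separate documents that may say more. All of this stands. It narrows the point, but it does not supply a route from a death classed as not study related to the AEAC.

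A reader might also infer more than the text supports:

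- **That adjudication can only revise harm downwards.** This does not follow. The AEAC gives the final seriousness and can move a filed event between Table 11-2 classes. The one-way feature concerns relatedness, for cases never filed.
- **That nothing called unrelated enters a safety rate.** TIA/stroke from follow-up forms does.
- **That such deaths can never be adjudicated.** No adverse event form is required for them, but none is forbidden. Section 11.3 limits only the adjudication of seriousness to reportable events.
- **That the overall rate must be biased low.** The stroke route carries no relatedness condition and could raise the rate, so the net direction is not established.
- **That no patient who died should count as event-free.** Counting every death as a failure would put confirmed unrelated deaths into an endpoint defined by relatedness.

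**Conclusion.** The point holds in a limited form. Deaths that the investigator classes as not study related, and non-stroke events called unrelated, require no adverse event form and have no specified route to AEAC relatedness review. For a death not filed as an adverse event, under-attribution cannot be corrected, while over-attribution of a filed event can. Death is not a listed safety outcome in SAP Tables 7 and 8.

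The size of any bias cannot be derived from the documents. On the assumption of a few missed patients, the effect on the overall complication rate is small beside its sampling error. The effect on related mortality matters more, since one case is the difference between none and some.

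The documents also disagree on whose judgement defines the endpoint. Protocol 4.4.2 gives it to the investigator, whereas protocol 11.3 and SAP 7.2.4 give it to the AEAC. These passages must be reconciled in any case.

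This is a cheap improvement to make, not a defect that invalidates the safety analysis.

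**What to change.** - **Protocol 11.1.1 and 11.3:** send every death recorded on an Exit form to the existing AEAC for adjudication of relatedness, whatever the investigator's class, and use the AEAC result for analysis.
- **SAP 8.2.1 and 8.2.2:** report all-cause death and AEAC-adjudicated related death at 30 days and 12 months in the BAS. Count only adjudicated related deaths in the procedure- and device-related rate. In the Kaplan-Meier analysis, censor unrelated deaths at the date of death instead of carrying them as event-free through 12 months.
- **Protocol 4.4.2:** reconcile the endpoint definition with protocol 11.3 and SAP 7.2.4.

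Non-fatal events called unrelated stay outside collection, as the registry intends. The report should say that for these the investigator's call is the starting point.

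The cost is short wording changes and a few extra cases for a committee that already exists, starting from Exit forms already completed. The related-event rate may come out slightly less favourable.
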